Group Cohesion Scale: The Group Cohesion Scale-Revised (GCS-R) will be used to measure group cohesiveness within the PeerFIT group intervention. The GCS is a 25-item multidimensional scale rated 1=strongly disagree to 4 = strongly agree assessing domains such as interaction and communication, member retention, decision making, vulnerability among group members, and consistency between group and individual goals.¹⁴

Medial Outcomes Study Social Support Survey: The 19-item Social Support Survey will be used to assess four components of perceived availability of social support among participants in both conditions, including (1) Emotional support/Informational support, (2) Tangible support (including material support), (3) Positive social interaction (does person have friends that are available to have fun), and (4) Affectionate support (including loving and nurturing relationships). A total score and subscale scores are calculated. Higher scores indicate more social support.¹⁵

Participant Characteristics and Covariates

Demographic Characteristics: Demographic characteristics will be collected with a client demographics instrument (CDI) developed by our research group. Socio-demographic information will include age, sex,

gender, race/ethnicity, living situation, education, employment status, and other basic characteristics.

Psychiatric Diagnosis: Psychiatric diagnosis will be verified using the diagnosis in the chart at the agency providing mental health services.

Medication Use: Because medications can directly affect weight gain and level of physical activity, we will collect self-report data on the type of prescribed psychiatric medications (e.g., antidepressant, antipsychotic) and all other medications taken by participants at the time of assessment. We will ask participants to bring their current medications with them to the assessment appointment. The research interviewer will document all current prescription and non-prescription medications taken by participants. In addition, the research interviewer will review a list of psychiatric medications and FDA-approved and non-approved weight loss medication to assess whether participants are currently taking any of the medications on the list.

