the number of posts, number of comments, and number of likes for each participant over the 12-month study duration. This data will be exported directly from the secret Facebook group to an excel document at 6-months and 12-months follow-up.

4. Analysis

Describe any qualitative tests and measures as well as quantitative methods:

Data Analyses

Analysis of data from the RCT will answer research questions associated with Specific Aims 1 and 2. Careful examination of frequency distributions and descriptive statistics for all variables will precede inferential statistical analysis. When necessary due to high skew, transformations will be used to normalize continuous data, or continuous variables will be recoded to ordinal or dichotomous scales.

Evaluation of Randomization. We will evaluate the effectiveness of random assignment by comparing the PeerFIT and BEAT groups on baseline measures of demographic characteristics, key outcome variables, and key covariates using chi-square tests and t-tests.

Handling of Missing Data. Based on our prior studies we do not expect attrition to exceed 20% over 12 months. The proposed method of analysis, mixed effects models, have been shown to produce unbiased estimates of treatment effect in the presence of data that is missing completely at random or missing at random even when dropout differs between treatment arms.¹⁸ We will also perform sensitivity analyses to examine stability of treatment effect under different missing data assumptions as recommended in case data are not missing at random (i.e., missingness depends on the value of the missing observation).

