3.6.5 Analyses for Study Aims and Hypotheses

Specific Aim 1 (Effectiveness): Mixed effects models will be fit to longitudinal weight, BMI, and cardiorespiratory fitness data. Models will include fixed effects for treatment arm, time and an interaction between treatment arm and time. Additionally, random individual-level intercept and slope terms will be included to account for individual variation in trajectory and simultaneously account for repeated observations within individual. A significant treatment effect of PeerFIT would be indicated by a significant time by treatment interaction accompanied by a mean reduction in weight or BMI or increase in fitness in the PeerFIT group that exceeds the reduction or improvement in the BEAT group (H1a). Similar, non-linear mixed effects models (i.e., longitudinal logistic models) will be fit to the binary cardiovascular risk reduction outcome data (H1b).

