Power Analysis for Aim 1. Assuming a range of within-person, across time correlations (0.1-0.7), with 144 participants (72 per arm), there will be 80% power, at the two-sided 0.05 significance level, to detect a difference between arms in slope of at least 0.030-0.052 SD units per month, or equivalently, 0.36-0.62 SD units over 12 months. If SDs of weight, BMI, and 6-MWT are similar to those observed previously (approximate weight SD 60, BMI SD 9, and 6-MWT SD 350) with the InSHAPE intervention and active control, these standardized effect sizes are equivalent to difference between arms of 21.6-36.0 lbs, 3.20-5.40 BMI units, and 6-MWT of 126-210m over 12 months. With attrition, power will be slightly lower, or equivalently, detectable differences slightly larger. To provide information on detectable differences if maximum attrition is experienced we also provide detectable differences assuming data from only 115 participants (80% of proposed sample size). In this case, the detectable difference increases to 0.034-0.059 SD units per month or 0.41-0.70 over 12 months yielding detectable weight of 24.6-42.0 lbs, BMI of 3.69-6.30, and 6-MWT of 143-245m over 12 months. True power/detectable difference likely lies in between for 144 vs. 115 participants. In the InSHAPE trial, 38% of participants in the active control arm and 51% of participants in InSHAPE achieved a clinically significant change in cardiovascular risk reduction. Because InSHAPE likely had a strong intervention effect with one-on-one personal fitness training and a gym membership for the active control, we estimate that percentages achieving clinically significant change in cardiovascular risk reduction in this study will be 20% for BEAT and 40% for PeerFIT. Assuming these proportions, there will be 86% power to detect a difference between arms in cardiovascular risk reduction, assuming measures of this outcome at 2 time points and within-person correlation of 0.5. With maximum attrition, the power is reduced to 77%.

Specific Aim 2 (Mechanism of Action): To test the mechanism hypotheses, parallel process latent growth curve models will be fit within a structural equation model (SEM) framework. These models allow for testing mediation of the treatment effect on weight and fitness by changes in self-efficacy (H2a) and peer social support (H2b). It is hypothesized that PeerFIT will have a greater effect on the change over time (slope) of

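### Aim 1 models leave out baseline medication, which the protocol itself says affects weight and activity; baseline significance tests cannot replace adjustment

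*Combined protocol and SAP*

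**What the plan says.** Three parts of the combined protocol and SAP bear on this.

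- **Section 4, Analysis, Evaluation of Randomization.** "We will evaluate the effectiveness of random assignment by comparing the PeerFIT and BEAT groups on baseline measures". The measures are demographic characteristics, "key outcome variables, and key covariates using chi-square tests and t-tests". No significance level, no size of imbalance that would matter, and no consequence for the analysis is given.
- **Section 3.6.5, Specific Aim 1.** "Models will include fixed effects for treatment arm, time and an interaction between treatment arm and time". Random intercepts and slopes are added for individuals. The logistic models for the binary risk-reduction outcome (H1b) are described as similar. No baseline covariate is named for either.
- **Section 3.6.2, Participant Characteristics and Covariates, Medication Use.** The reason given for collecting the data is: "Because medications can directly affect weight gain and level of physical activity". Table 1 schedules the medication list at months 0, 6 and 12, and interviewers also check a list of psychiatric and weight-loss medications.

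The only other planned use of a covariate that I found is fidelity data (section 3, Fidelity Measurement), described as a potential covariate and measured after randomisation.

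**The concern.** The protocol identifies medication as a direct influence on the Aim 1 outcomes, lists it under covariates and measures it before treatment, but the models for those outcomes do not name it. The population will vary on it: the eligibility criteria bar only recent starts of two antipsychotics, and use of weight-loss medication is unrestricted. The one place where baseline covariates are compared between arms is a set of significance tests.

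Those tests answer a different question. If allocation was properly random, every baseline difference arose by chance, so a p-value cannot show whether assignment worked. Nor does a non-significant result at this sample size show that a prognostic factor is balanced. What matters for the treatment comparison is how strongly the factor predicts outcome, and a model term deals with that whatever the baseline table shows.

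At stake is some precision in H1a and H1b, and protection in the particular trial where a chance medication imbalance occurs.

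**Working it through.** **Inputs from the documents.** 144 participants, 72 per arm, and "80% power, at the two-sided 0.05 significance level" (section 3.6.5, Power Analysis for Aim 1); visits at 0, 6 and 12 months; H1b rates of 20% and 40%, two time points, within-person correlation 0.5.

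**Assumed, because the documents do not say.** Two-sided 0.05 for the baseline tests; the true imbalances used as examples; the correlation r between baseline medication status and outcome change.

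**1. The plan's own power figures, which use no covariate.**

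- Detectable slope difference = (1.960 + 0.842) × √[2(1 − ρ)/(72 × 72)]. One 72 is the number per arm; the other is the sum of squares of the visit times about their mean (36 + 0 + 36). This gives 0.0522 SD per month at ρ = 0.1 and 0.0301 at ρ = 0.7. Stated: 0.030 to 0.052.
- H1b: effective number per arm = 72 × 2/(1 + 0.5) = 96, power 86.2%. Stated: 86%. With 115 participants, 57.5 × 2/1.5 = 76.7, power 77.7%. Stated: 77%.

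The figures reproduce, so the sample size is a sound base for the rest.

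**2. What the baseline tests can see at 72 per arm.**

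- t-test (noncentral t, 142 degrees of freedom): a true difference of 0.2 SD is missed 78% of the time, 0.3 SD 57%, 0.5 SD 15%.
- Largest non-significant observed difference = 1.977 × √(2/72) = 0.33 SD.
- Chi-square (full binomial enumeration): 40% versus 55% is missed 54.5% of the time, or 61% with continuity correction; 40% versus 60% is missed 31%, or 37% with correction.

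Only large imbalances are reliably seen.

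**3. What adjustment would gain.** For a comparison of change between randomised arms, adjusting for a baseline covariate with correlation r multiplies residual variance by 1 − r². The equivalent number of extra participants is 144 × r²/(1 − r²).

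| Assumed r | Variance reduction | Equivalent participants | Power of an 80% comparison becomes |
|---|---|---|---|
| 0.2 | 4% | 144 × 0.04/0.96 = 6.0 | 81.6% |
| 0.3 | 9% | 144 × 0.09/0.91 = 14.2 | 83.6% |

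The last column is Φ[(1.960 + 0.842)/√(1 − r²) − 1.960]. These figures fit the continuous outcomes of H1a; for the logistic H1b model they are only a rough guide.

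**4. Does the unadjusted test lose its 5% error rate?** Given a covariate imbalance of z₀ standard errors, the unadjusted test statistic under no effect is N(r z₀, 1 − r²).

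- At the edge of non-significance, z₀ = 1.9, two-sided error is 6.2% at r = 0.2, 7.7% at r = 0.3 and 12.2% at r = 0.5. Values of |z₀| between 1.90 and 1.96 occur in about 0.7% of randomisations.
- Averaged over all non-significant imbalances (|z₀| < 1.96), the error is 4.9%, 4.7% and 4.3% at the same r.

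So there is no inflation on average, and following a non-significant baseline test the unadjusted comparison is slightly conservative.

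**5. Which model term is needed.** H1a is judged on the arm-by-time interaction. A medication main effect alone shifts all visits equally and would change that test little; the term that matters is medication by time. H1b is already defined as change from baseline, so a main effect suffices there.

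**The case against.** The strongest reply is that randomisation makes the unadjusted comparison valid without covariates, that the baseline tests enter no Aim 1 inference, and that no document shows medication status predicts change in weight or fitness. The first two parts stand in full. The third stands as a limit on size: the gain depends on r, which is why a range is shown.

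A reader might infer more than the documents support:

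- **That the plan treats non-significance as balance, or significance as failed randomisation.** It states neither rule, and links no result to later adjustment.
- **That false-positive error is inflated to 8% to 12%.** That holds only near z₀ = 1.9 with r of 0.3 to 0.5; step 4 shows the average stays just under 5%.
- **That a baseline weight gap of 0.33 SD, about 20 lb at the plan's SD of 60, would pass unnoticed into the H1a result.** Baseline weight is the time-0 response in the longitudinal model, so such a gap is largely handled there.
- **That some baseline test will probably be significant by chance.** With independent tests the probability is 40% for 10 and 72% for 25, but the plan tests only key outcomes and covariates plus demographics and gives no count.
- **That medication is not controlled at all.** Recent starters of olanzapine or clozapine are not eligible, and section 9 says randomisation is stratified. The stratification factors are not visible in the text available, so nothing is inferred about them.

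What remains is that the plan names a prognostic factor, measures it at baseline, and does not use it in the Aim 1 models.

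**Conclusion.** The concern holds as a modest improvement, not as an error in the plan. The Aim 1 models name no baseline covariate although the protocol calls medication a direct influence on the outcomes, and the chi-square and t-tests are too insensitive, and aimed at the wrong question, to take the place of adjustment. The cost of leaving it out is about 4% to 9% of variance, or 6 to 14 participants out of 144, if r is 0.2 to 0.3; less if medication status predicts change more weakly. There is also no protection in the individual trial where a chance imbalance occurs. The size rests on that assumed correlation, and the miss rates on an assumed two-sided 0.05 for the baseline tests. Replacing those tests would not by itself change any Aim 1 result; the substance of the point is the missing model term.

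**What to change.** **Main change, section 3.6.5, Specific Aim 1.** Before unblinding, prespecify baseline weight-affecting medication status as a covariate, for example antipsychotic use (yes/no) and weight-loss medication use (yes/no). In the H1a models include each with its interaction with time. In the H1b logistic model include each as a main effect. Keep the terms whatever the baseline table shows.

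**Accompanying reporting change, section 4, Evaluation of Randomization.** Present baseline values by arm with standardised differences, as description, in place of significance tests. Judge whether assignment worked from the allocation records.

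**Cost.** SAP wording and a few degrees of freedom: with two binary covariates and linear time, four coefficients in H1a (two main effects, two interactions) and two in H1b. The data are already scheduled at month 0. The H1b odds ratio becomes conditional on the covariates; reporting standardised proportions by arm alongside it keeps the result readable.

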3.6.5 Analyses for Study Aims and Hypotheses

Specific Aim 1 (Effectiveness): Mixed effects models will be fit to longitudinal weight, BMI, and cardiorespiratory fitness data. Models will include fixed effects for treatment arm, time and an interaction between treatment arm and time. Additionally, random individual-level intercept and slope terms will be included to account for individual variation in trajectory and simultaneously account for repeated observations within individual. A significant treatment effect of PeerFIT would be indicated by a significant time by treatment interaction accompanied by a mean reduction in weight or BMI or increase in fitness in the PeerFIT group that exceeds the reduction or improvement in the BEAT group (H1a). Similar, non-linear mixed effects models (i.e., longitudinal logistic models) will be fit to the binary cardiovascular risk reduction outcome data (H1b).

Power Analysis for Aim 1. Assuming a range of within-person, across time correlations (0.1-0.7), with 144 participants (72 per arm), there will be 80% power, at the two-sided 0.05 significance level, to detect a difference between arms in slope of at least 0.030-0.052 SD units per month, or equivalently, 0.36-0.62 SD units over 12 months. If SDs of weight, BMI, and 6-MWT are similar to those observed previously (approximate weight SD 60, BMI SD 9, and 6-MWT SD 350) with the InSHAPE intervention and active control, these standardized effect sizes are equivalent to difference between arms of 21.6-36.0 lbs, 3.20-5.40 BMI units, and 6-MWT of 126-210m over 12 months. With attrition, power will be slightly lower, or equivalently, detectable differences slightly larger. To provide information on detectable differences if maximum attrition is experienced we also provide detectable differences assuming data from only 115 participants (80% of proposed sample size). In this case, the detectable difference increases to 0.034-0.059 SD units per month or 0.41-0.70 over 12 months yielding detectable weight of 24.6-42.0 lbs, BMI of 3.69-6.30, and 6-MWT of 143-245m over 12 months. True power/detectable difference likely lies in between for 144 vs. 115 participants. In the InSHAPE trial, 38% of participants in the active control arm and 51% of participants in InSHAPE achieved a clinically significant change in cardiovascular risk reduction. Because InSHAPE likely had a strong intervention effect with one-on-one personal fitness training and a gym membership for the active control, we estimate that percentages achieving clinically significant change in cardiovascular risk reduction in this study will be 20% for BEAT and 40% for PeerFIT. Assuming these proportions, there will be 86% power to detect a difference between arms in cardiovascular risk reduction, assuming measures of this outcome at 2 time points and within-person correlation of 0.5. With maximum attrition, the power is reduced to 77%.

Specific Aim 2 (Mechanism of Action): To test the mechanism hypotheses, parallel process latent growth curve models will be fit within a structural equation model (SEM) framework. These models allow for testing mediation of the treatment effect on weight and fitness by changes in self-efficacy (H2a) and peer social support (H2b). It is hypothesized that PeerFIT will have a greater effect on the change over time (slope) of

self-efficacy than BEAT, and this change in self-efficacy will impact change in weight and fitness over time (slopes). PeerFIT is hypothesized to have a greater effect on peer social support slope than BEAT, and this change will also impact the change in outcomes. The product of coefficients (coefficient associated with path between treatment and mediator x coefficient associated with path between mediator and outcome) will be estimated along with bias-corrected bootstrap confidence intervals to determine the significance of the effect.

Power Analysis for Aim 2. The mechanism to be tested is the indirect effect of treatment on changes in weight and fitness (outcomes) through changes in self-efficacy and changes in peer social support (proposed mediators). The power for detection of the indirect effect depends on the size of each effect in the pathway.

The proposed parallel process growth curve analysis proposes mediation of the individual latent slopes, so power is computed at the individual-level although the individual-level latent slopes are estimated using data from observed mediators and outcomes measured at three time points (0, 6, and 12 months) improving precision. To compute power for detecting the mediated effect, we use results of a simulation study conducted by MacKinnon et al. In the simulation, indirect effects composed of effect of treatment on mediator and mediator on outcome were varied in size and significance was repeatedly tested via bias-correct bootstrap confidence intervals to obtain estimates of empirical power. This study showed that with 144 participants there will be approximately 80% power to detect a significant effect if the mediated effect is made up of two effects that are halfway between small and medium as defined by Cohen (explaining about 6.3% of the variance). For example, if treatment explains at least 6.3% of the variance in changes in self-efficacy, and changes in self-efficacy explain at least 6.3% of the variance in changes in weight, then there will be 80% power to detect this effect via bias-corrected bootstrap confidence intervals constructed around the indirect effect of treatment on changes in weight. If at least one of the effects (treatment to mediator or mediator to outcome) is larger (at least a medium effect explaining 13% of the variance), power is greater than 80%.

Qualitative Interviews Analysis. A semi-structured interview format will be used to allow flexibility in sequencing of questions and to allow for additional probing to clarify responses. Interviews will be audio-recorded. Audio files will be transcribed and de-identified by a professional transcription company. Transcripts will then be uploaded into a qualitative coding software program, Atlas.ti. Qualitative data analysis will include coding the data and identifying themes and salient points that illustrate the experiences of no engagement, low engagement, and high engagement participants in the study.

5. Study Progress Monitoring

Note: appropriate monitoring may include periodic assessment of the following:

- data quality
- timelines
- recruitment and enrollment

Provide a description of the methods which will be used to determine the progress of the study, including periodic assessments of data quality, timelines, recruitment, and enrollment as appropriate:

The trial consists of three main phases: planning, implementation (recruitment, intervention and data collection) and data analysis and dissemination. Hiring and training research coordinators, interviewers, and lifestyle coaches, and planning for implementation of the study protocol at research sites will occur during the first 6 months. Recruitment of participants will begin in month 6 and will conclude in month 33 or earlier, depending on when recruitment targets are met. We plan to recruit 144 participants. Participants will be enrolled on a rolling basis. The 12-month follow-up assessments will be completed by month 42, allowing 6 months for data cleaning, analysis, and manuscript preparation (months 42-48). The study timeline and enrollment milestones are shown below:

Month	YEAR 1				YEAR 2				YEAR 3				YEAR 4			
	0-3	3-6	6-9	9-12	12-15	15-18	18-21	21-24	24-27	27-30	30-33	33-36	36-39	39-42	42-45	45-48
Hire/Train Personnel																
Finalize Study Procedures																
Prepare Agency for Implementation																
Study Recruitment																
Recruitment Milestones				24	48	64	80	96	112	128	144					

Assessments											
Data Analysis											

To monitor study recruitment and enrollment, the PI ([name]) will lead a weekly supervision call with the research coordinator and research interviewers to monitor progress and regularly address questions and problems that arise during recruitment. Our approach to assessing data quality includes: 1) monitoring counts of completed data collection items; 2) monitoring distribution of trial outcomes, overall, by data collector and site; 3) record lag time in data entry; 4) issue queries on missing data, out of range values or illogical data relations; and 4) review types and distribution of data entry errors. Weekly research team conference calls, including assessment supervision, will help identify quality control issues early and allow consensus solutions to be reached.

Data Safety and Monitoring Plan: Although there is a low risk of adverse events (AE) associated with gradual, supervised weight loss and moderate exercise in young adults, an independent data safety monitoring process will be implemented for the proposed clinical trial. An independent Data Safety Monitoring Board (DSMB) will conduct reviews of the study every 12 months to ensure the safety of participants and data validity and integrity. The established DSMB that will be used for this study consists of several federally funded, highly experienced clinical researchers in the Department of Psychiatry at the Geisel School of Medicine at Dartmouth. Current members of the DSMB consist of researchers who are not co-investigators or collaborators on this proposal. This independent board will follow the policy for data and safety monitoring published by NIH.

The DSMB will be responsible for reviewing the following information: adverse consequences (whether serious or minor) to any participant and actions taken to remedy the problem; data quality, completeness, timeliness; performance of the study site; recruitment and retention; adherence to protocols; maintenance of confidentiality; external factors impacting safety or ethics of the study; and new or evolving information regarding the expected effectiveness and/or safety of the PeerFIT intervention. Summary reports of the meetings will be sent at the time of annual reviews to the Dartmouth Committee for the Protection of Human Subjects (CPHS).

6. Risks & Benefits

Note: Risks may be physical, psychological, social, legal, economic, to reputation, or others.

a. Describe any potential risks, their likelihood and seriousness:

Physical activity. The intervention emphasizes the achievement of moderate, not vigorous intensity physical activity; the safety of moderate intensity physical activity in young adults with no prior cardiac event and no anginal symptoms is well established. The small risk of physical activity will be minimized by emphasizing moderate (as opposed to vigorous) activity, and requiring participants who screen for elevated CVD risk to obtain medical clearance prior to beginning an exercise program. Risk of injury is further minimized by instruction on proper exercise technique, the importance of warm-up and cool-down exercises, and proper stretching techniques. If there is any question about the etiology of an injury or the need for treatment, the participant will be referred to a physician for further evaluation. We will continuously reinforce our recommendation to engage in moderate physical activity throughout the program duration.

Nutrient intake. Calorie reduction for weight loss could theoretically lead to inadequate nutrition or excessive, rapid weight loss. Intervention subjects will be encouraged to eat a variety of foods from all food groups and maintain an adequate caloric level. The lifestyle coach will conduct a private weigh-in at the beginning of each weight management and exercise session. Participants who have a sudden, marked weight reduction will be interviewed to determine if extreme measures have been taken. The issue of adequate nutrient intake and the importance of safe weight loss will be discussed in the group sessions. If a problem is suspected, the participant will be referred to their primary care physician and their primary mental health provider at the MA DMH, MHCGM, GNMHCCC, or CMHA study sites for follow-up.

Group activities. The potential minimal risks of participating in groups include potential stress surrounding sharing personal information in a group setting and hearing about the life experiences of others. The group leaders will lay out the ground rules for participating in the groups, such as not sharing personal or sensitive information about group participants with people outside of the group, and treating each other respectfully and cordially. Intervention staff will receive regular supervision and training from the PI ([name]) that will provide opportunities to address any concerns or ongoing problems associated with group dynamics. For more acute situations requiring immediate assistance, intervention staff will be instructed to contact the site coordinator and site PI. Additionally, intervention staff will be given a list of study participants' names and their respective primary mental health providers in case a problem arises that requires intervention by the mental health agency. These latter protections were used in our PeerFIT pilot study and were very rarely needed, but promptly and safely resolved any issue.

Text messaging. The text message component of this study poses minimal risk to participants. Participants are sent text messages from the PeerFIT lifestyle coach and BEAT lifestyle coach 3-5 times per week over the 12-month intervention period. PeerFIT related text messages contain content to promote program attendance to the weekly group sessions and exercise classes, and to increase motivation for small goal changes related to healthy eating and being physically active. The BEAT related text messages will include reminders and encouragement for self-monitoring weight loss behaviors. The text messages are structured in the same way for each participant, with only minor customizations according to first name, gender, and other personal characteristics. The text messages will not contain any personally identifying information (except for participants' first names) or any information pertaining to participants' specific mental health conditions or diagnosis.

Fitbit activity tracker. The Fitbit activity tracker poses minimal, if any, risks to participants. The device is worn on the wrist or by attaching it to participants' clothing, or keeping it in participants' pockets, and is designed to monitor steps walked and overall participation in physical activity. The device itself does not collect or contain any personal information. Each participant will create an online Fitbit account that will only contain participants' names, email address (which is their Fitbit username), gender, age, height, and weight. No other personally identifying information regarding each participant is stored within the online profile. Individual usernames and passwords for the online profile will only be known by research staff and respective participants. Fitness data will be collected from the device over a secure electronic connection and will be stored in the user's online account that synchs with the device through the smartphone application. Participants will also have the option to use other features on the Fitbit smartphone application such as viewing physical activity over time, tracking sleep, or tracking dietary intake. Using the app is optional but encouraged. Research members will not share Fitbit data from participants with other study participants. However, participants can choose to connect with other participants using the Fitbit smartphone "friend" feature built into the Fitbit app to share information such as step count and distance traveled. Participants can also choose to share their steps or progress meeting their step goals with other participants using the secret Facebook group.

Fitbit account usernames (i.e., email address), Fitbit account passwords, and study IDs will be stored on a password-protected spreadsheet that is maintained by and accessible to only the research team. This information will be used by research staff to connect Fitbit accounts on a data management platform called Fitabase. Fitabase is fully hosted, cloud-based software that follows industry standards to maintain secure databases and keep data private. Once a Fitbit account is connected to the Fitabase platform by research staff by registering the user's Fitbit username and password, it will be assigned a unique study ID – the participant's ID in the study – along with a "start" and "stop" synch date so that data will be synched only during the participant's 12-month participation and available for viewing and downloading by research staff in de-identified form. Fitabase does not collect or retain any identifiable information, such as the Fitbit user's email address, "Friends" list, IP address, or any GPS data. When participants synch their devices to their Fitbit accounts, Fitabase will collect this new information automatically. Given that participation in this study is voluntary, participants can also choose not to connect their Fitbit accounts with Fitabase. If participants choose not to connect their Fitbit account with the Fitabase data management platform, it will not affect their participation in the study or their access to using a Fitbit wearable device as part of their participation.

Data collected by Fitabase is housed in secure Azure (Microsoft) servers. Windows Azure runs in data centers managed and operated by Microsoft Global Foundation Services (GFS). These geographically

dispersed data centers comply with industry standards, such as ISO/IEC 27001:2005, for security and reliability. Furthermore, Fitabase database servers are IP firewalled and whitelisted such that they refuse any connection from IP addresses not preprogrammed as acceptable. Fitabase does not sell, release, or make collected data available to third parties. The data collected for a research team is only made available to that research team. In circumstances that dictate it, Fitabase staff may access participant data in order to provide technical support. Fitabase uses Secure Sockets Layer (SSL) for all logins, billing, and administration of the site. Fitabase stores passwords in encrypted form. Fitabase logs all site usage, including attempts to access restricted data or repeated erroneous logins. Fitabase will freeze accounts that appear to be compromised until they are able to make contact via the email address used to set up the administrator account. Per Fitabase's security policy, participants' de-identified accounts will be deleted from the Fitabase platform 90 days following the completion of data analysis for the study.

Secret Facebook Group. The secret Facebook group created for this study also poses minimal risk to participants. The Facebook group will be secret and only visible and accessible to participants who are invited to join by the research staff. Participants will have the choice to access the secret Facebook page using either their own smartphone, or if they do not have one, a smartphone provided by this study. All participants in this study randomized to the PeerFIT intervention, regardless of their prior experience using Facebook, will be provided with a basic overview of the Facebook website and mobile smartphone application, as well as safety precautions with using this online platform. Participants will be provided with safety recommendations, such as not sharing personally identifying information online that they do not wish other people to see, including phone number, address, financial information, or detailed health information. Participants will also receive recommendations about not responding to friend requests from strangers, ways to block or unfriend Facebook users that appear to be spam or junk accounts, and how to report content viewed as inappropriate to the Facebook website. For participants who are not familiar with Facebook or who do not have Facebook accounts, research staff will provide training about how to create a free account and how to use the website safely without disclosing personal health information or other personal information.

Participants will be oriented to the safety resources available from the Facebook website. Participants will be provided a live demonstration of the Facebook safety website at: <https://www.facebook.com/safety>.

On this page, participants will be guided through a ways to stay safe while using Facebook. This will include instruction about 1) Sharing; 2) Friending; and 3) Reporting.

1) Sharing:

"Every day, people around the world share things on Facebook that result in new and incredible ideas, opportunities, friendships and collaborations."

"We ask people to consider their audience when sharing on Facebook. It's important to be thoughtful about how and what you share. We make it easy for everyone to decide who can see the content they share, and we have policies that prohibit hateful, violent or sexually explicit content."

Before you share, ask yourself:

- Could somebody use this to hurt me?
- Would I be upset if someone shared this with others?
- What's the worst thing that could happen if I shared this?

"Always remember that the things you share with your friends can end up being shared with others."

2) Friending

"Facebook is a place for you to connect with the people and things you care about. Before accepting someone as a friend, you might want to take a look at the person's profile. Have you ever met them in person? Do you have friends in common?"

Following

"When you follow someone, you can see their posts in your News Feed. You automatically follow people you're friends with. You can also follow the posts of public figures (ex: journalists, celebrities, political figures) even if you're not friends."

Unfollowing

"When you unfollow someone, you won't see their posts in your News Feed, but you'll still be friends with them."

"To unfollow a person, Page or group directly, hover over "Following" (on a profile) or click "Following" (on a Page or in a group) near their cover photo and select "Unfollow"."

Unfriending

"To unfriend someone, go to that person's profile, hover over the "Friends" button at the top and select "Unfriend". If you choose to unfriend someone, Facebook won't notify the person but you'll be removed from their friends list. If you want to be friends with this person again, you'll need to send a new friend request."

Blocking

"You can block someone to unfriend them. This will prevent them from starting conversations with you or seeing things you post on your profile. In addition, people you block can no longer tag you, invite you to events or groups, or add you as a friend. Blocking is reciprocal, so you also won't be able to see things they post or start conversations with them. When you block someone, we don't notify them."

"To block someone, click  at the top right of any Facebook page, click "How do I stop someone from bothering me?", enter the name or email address of the person you want to block and click "Block.+"

3) Reporting

